Study Design:	
This is an interventional parallel group (AA and other (race) veterans) efficacy study of AUTOPAP (standard first- line) treatment in 220 veterans with OSA. Patients will be enrolled consecutively to reach target enrollment of 110 in each group. All outcomes assessment will be done 3 months after AUTOPAP treatment initiation.
 
Recruitment Site: Sleep, Tele-sleep (for Adam Benjamin Jr CBOC), Pulmonary, and Primary Care Clinics at JBVAMC. In addition, local IRB approved study flyers will be posted in sleep and pulmonary clinics at Hines and North Chicago VA.
 
Initial Screening Visit #1: At the first clinic visit, each patient will be provided with oral and written information (informed consent form) describing the study and will

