Exploratory Endpoints:	
 7. Test association of genetic ancestry with endpoints 1 to 3. 8. Test association of myocardial mechanical data from TTE with AHI (OSA severity). 9. Generate effect size estimates for change in myocardial mechanics with 3 months of AUTOPAP treatment.
-------------------------------	---

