Tissue banking: blood processing for DNA, RNA, serum and plasma isolation and storage will be performed at UI Biorepository, under the supervision of [name], [name] and [name] (Clinical Science Building North, [name]). The blood samples to be carried outside JBVAMC will be labeled with unique study ID number only. Only the processing of blood will be done outside JBVAMC and the blood draw procedure will only be done at JBVAMC. The processing for JBVAMC is done at the Madison/Milwaukee VA lab. To avoid delays loss of sample or sample integrity, we want to hand-deliver the samples without individual identifiers to UIC for prompt processing.

- viii. **Echocardiogram** data will include myocardial mechanical data obtained by clinical software that is used in the clinical workstation in the JBVAMC echocardiography laboratory. This software is called Velocity Vector Imaging (VVI; Siemens Medical Solutions USA, Inc., Mountain View, CA). [name], JBVAMC cardiologist and collaborator will provide interpretation of these data.

Visit #2: Patients performing home PM will be instructed to begin ABP monitoring and urine sample collection the morning prior to the scheduled visit 2. Visit 2 will be in the morning and PM device, actigraphy, sleep log, urine sample, and ABP monitor will be collected and processed/downloaded. Patients performing PM test at JBVA will be instructed to begin ABP monitoring and urine collection the morning of scheduled visit 2. Patients will arrive for the overnight PM at JBVAMC. Actigraphy, sleep log, urine sample, and ABP monitor will be collected and processed/downloaded in the morning after completion of the PM test. PM tests will be performed using ALICE PDX (Phillips Respironics) or WatchPAT200 (Itamar Medical). PI has experience with both these devices that are available to us, are validated, used routinely in

clinical practice, and provide similar information with respect to screening for OSA. All patients with apnea hypopnea index (AHI) ≥ 15 /hour on the PM test will be invited to continue. This additional screening step with PM testing will reduce screen failure rates with PSG, which is more costly. We propose to allow both home PM and PM at JBVAMC in order to minimize scheduling conflicts between clinical and research tests scheduled.

Previously scheduled Visit 3 will be eliminated to reduce participant burden and improve recruitment to meet target sample of 220 over the next two years.

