7.3 Withdrawal from Study Treatment Due to Adverse Experience

Patients withdrawn from receiving additional study drug due to an AE will be followed by the PI until resolution or stabilization of the event. Additional reports will be provided to the regulatory authorities when requested. Every effort will be made to follow the patient for the full study period as per the schedule of study visits.

8. Final Outcomes Assessment:

Table. Outcomes and covariates
Outcomes
Specific Aim 1. Between Group Comparisons (African Americans vs. Other): Measure change from pre-treatment to 3 months after AUTOPAP treatment: (a) Primary - average 24-hour systolic and diastolic BP (b) Secondary - central aortic blood pressure ii. average of 24-hour mean BP = diastolic + 1/3x (systolic - diastolic) iii. 24-hour urine norepinephrine & normetanephrine iv. Overnight urine 8-isoprostane levels
Specific Aim 2. (change from pre-treatment to 3 months after AUTOPAP treatment): (a) Primary (between-group comparison) - change in number of PVT lapses (b) Secondary (within-group comparisons) - i. Association of change in PVT lapses with primary outcome of specific aim 1. ii. Association of change in PVT lapses with secondary outcomes of specific aim 1. iii. Association of change in ESS scores with outcomes of specific aim 1.
Exploratory Aim 3. i. Within-group analysis of change in specific aim 1. primary and secondary outcomes (i. and ii.) with addition of Individual Ancestry as a covariate. ii. Velocity Vector Imaging (VVI) from echocardiography correlation with AHI. iii. Generate effect size estimates for AUTOPAP treatment on VVI.
Covariates: Specific Aims 1 and 2
Socio-demographic Characteristics 
 • Age (continuous) • Daily sleep duration on actigraphy (continuous) • Gender (categorical, 2 levels) • Education (categorical, 2 levels; ≤ high school, > high school) • Income per annum (categorical, 5 levels; <30K, 30-50K, 51-75K, 76-100K, >100K) • Smoking status (pack-years; continuous) • Alcohol use (number of drinks/week; continuous)
OSA Disease Severity 
 • AHI • Time below 90% oxygen saturation (T<90)
Co-morbid Medical Conditions 
 • Obesity: Body Mass Index (BMI) • General Health Status: Charlson Comorbidity Index (CCI)

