9.4 Statistical Analyses

9.4.1 Power and Sample Size Estimation: The primary goal of this initial study is to estimate differences in the effect size of AUTOPAP treatment on ABP and CABP in AA and EA's with moderate to severe OSA. Our preliminary data shows a reduction in office BP 3 months after AUTOPAP treatment and the effect size difference between-groups (by ethnicity; using differences in mean \pm SD change of BP and t-tests in PASS program, <http://www.ncss.com/pass.html>) was 0.42 for systolic and 0.53 for diastolic blood pressure. We determined that 99 patients in each group (total n = 198) will provide power of 0.8 in two-tailed tests with an alpha of 0.05 to observe a difference in effect size between groups of 0.4. Based on our prior experience we anticipate an attrition rate of 10-20%. Therefore, a total of 220 (198/0.90) patients enrolled will achieve the target of 198 patients completing the study. Our preliminary study of PM in our clinical population (selected with a positive BSQ) shows approximately 95% sensitivity and specificity of PM determined AHI of ≥ 15 /hour in terms of predicting PSG-determined AHI of ≥ 15 /hour (inclusion criteria). Therefore, we expect to screen approximately 260 patients (220/0.95).

9.4.2 Data analysis: A p-value < 0.05 will be considered significant. All variables and analysis goals are listed in table above. **Specific Aim 1.** Within group changes in primary and secondary outcomes will be assessed with repeated measures ANOVA implemented with PROC MIXED in SAS. A two-sample t-test (PROC TTEST in SAS) will be used to examine between-group differences in the treatment-related changes in primary and secondary outcomes. **Specific Aim 2.** Primary outcome will be assessed with a two-sample t-test (PROC TTEST in SAS). Secondary outcomes will be assessed with partial correlations implemented with PROC CORR in SAS.

Exploratory Aims 3. Effect of Individual Ancestry on changes in primary and secondary outcomes of specific aim 1 within group will be assessed with ANCOVA implemented with PROC GLM in SAS. Correlations (of VVI with AHI and change in VVI with change in AHI) will be assessed within groups.

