The proposed research might not be of direct benefit to the subjects but is of potential benefit to society by increasing our understanding of the effectiveness of AUTOPAP treatment in reducing adverse cardiovascular outcomes of obstructive sleep apnea. Potential benefits to the subjects in this preliminary study include favorable effects on nightly sleep, excessive daytime sleepiness, blood pressure control, and cardiovascular risk. Moreover, if data obtained from the subjects in this preliminary study shows improvement of biomarkers implicated in progression of blood pressure and ambulatory blood pressure levels, this will lead to the design and implementation of larger studies to evaluate the effect of this AUTOPAP intervention on cardiovascular disease progression. Overall, we feel that the benefits of this research greatly outweigh the risks to the subjects.

D. Importance of the Knowledge to be Gained

The overall objective of our proposal is to examine continuous positive airway pressure treatment-related effects on adverse cardiovascular effects (including 24-hour blood pressure profile) of obstructive sleep apnea in African Americans, a high-risk population. The ability to identify and effectively intervene for poorly-controlled hypertension in this population is of great relevance as it could help reduce the progression of organ injury.

E. Data and Safety Monitoring Plan

Safety Monitoring: Data from the study will be monitored on a continuous basis by the Data Safety Monitoring Committee [[name], principal PI (PI), Drs. [name], and [name] (mentors), study coordinator [name]]. All serious adverse events (SAEs), adverse events (AEs), and laboratory values will be reviewed by the PI on an ongoing basis. The PI will be responsible for annual reports to the I.R.B and for reporting any adverse events (AEs) to the IRB. The IRB will be notified within 24 hours of any SAE occurring. In addition, all laboratory values outside of normal range will be discussed with the study subject, and appropriate arrangements will be made for treatment, if necessary. The data monitoring and safety committee composed of Drs. [name], [name], and [name] will meet on a monthly basis to discuss all safety issues. All key personnel involved in the conduct of the research proposed will receive the required education of the protection of human research subjects prior to starting work on this project.

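### No masking to visit or AHI is specified for the cardiologist reading the research echoes, so reader expectation could bias the exploratory VVI effect size and the VVI-AHI correlation

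*Combined protocol and SAP*

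**What the plan says.** Section 3, item viii, describes how the echo data arise: "Echocardiogram data will include myocardial mechanical data obtained by clinical software that is used in the clinical workstation", in the JBVAMC echocardiography laboratory, using VVI. A "JBVAMC cardiologist and collaborator will provide interpretation of these data".

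These readings serve two planned results:

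- **Pre-post effect size.** The synopsis (Exploratory Endpoints) has "Generate effect size estimates for change in myocardial mechanics with 3 months of AUTOPAP treatment", and the Section 8 table, under Exploratory Aim 3, has "Generate effect size estimates for AUTOPAP treatment on VVI".
- **Relation to OSA severity.** The synopsis has "Test association of myocardial mechanical data from TTE with AHI (OSA severity"). Section 9.4.2 adds: "Correlations (of VVI with AHI and change in VVI with change in AHI) will be assessed within groups".

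The synopsis also lists reversibility of abnormal myocardial mechanics as a secondary objective (number 6), although the matching endpoints are labelled exploratory.

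On allocation, the synopsis says: "This is an interventional parallel group (AA and other (race) veterans) efficacy study of AUTOPAP". The two groups are defined by race, all participants are treated, and there is no untreated or sham arm.

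**The concern.** In a single-arm before-and-after comparison, the order of the scans is the treatment status. If the reader can see the scan date, the reader knows which scan followed three months of AUTOPAP.

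The plan also says which way the result is expected to go. Section 2.2 reports limited data suggesting that positive airway pressure may improve myocardial mechanics, and it presents speckle-tracking as a way to pick up subtle preclinical change. Small expected changes are the ones most easily shifted by a reader's expectation. The same section calls the relation between deformation and OSA severity inconsistent. A reader who knows the AHI could tilt that relation too.

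At stake is the credibility of the echo results. They consist of effect-size estimates and correlations, and they come from readings for which the plan describes no safeguard.

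**Working it through.** **1. Where the plan specifies coding, and where it does not.**

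| Material | Provision in the plan |
|---|---|
| Overnight urine (Section 3, item vii) | Labelled with study ID and sample type only |
| Blood (Section 3, tissue banking) | Labelled with study ID only when carried outside JBVAMC |
| Statistical dataset (Section 9.3) | Identifiers removed before analysis, when the readings already exist |
| Echo images and VVI reading (Section 3, item viii) | No coding, masking, reading order or second reader described |

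Appendix IV (B.2) also promises study codes for source documents and specimens, but as a confidentiality measure. It does not hide visit or AHI from a reader.

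**2. Scan order and treatment.** All participants start AUTOPAP at visit 3, and a repeat echo is planned only for those who had a pre-treatment one. Second scan therefore means treated scan. One caveat: Section 3 asks for the baseline echo before visit 4, while AUTOPAP set-up is now at visit 3, so a baseline scan could fall after treatment start. Those statements need to be reconciled. That is a separate matter from masking.

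**3. The plan's own sample-size figure.** Section 9.4.1 states 99 per group for a between-group effect size of 0.4, power 0.8, two-sided alpha 0.05. The normal approximation gives n = 2 × (1.96 + 0.84)² / 0.4² = 98, or 99 with unrounded quantiles and rounding up. Exact t-test power at 99 per group is 0.7997. Enrolment is 198 / 0.90 = 220. The figures reproduce, but they concern blood pressure. The plan gives no echo sample size, SD or expected change, and echo is optional, so there is no echo figure to check.

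**4. Effect of a reader shift on the pre-post result.** Let δ be the true mean change divided by the SD of change, and b a systematic reader shift in the same units. A constant shift leaves the SD unchanged, so

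recorded standardised effect = δ + b.

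The bias is b, and it does not shrink as more patients are scanned.

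**5. Sensitivity only.** Both the number of echo pairs N and the shift b are assumptions. With no true change (δ = 0), the normal approximation for a paired test gives

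P(two-sided p < 0.05) = Φ(b√N − 1.96) + Φ(−b√N − 1.96),

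and the 95% confidence interval half-width is 1.96/√N.

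| Pairs N | Half-width (SD) | b = 0.1 | b = 0.2 | b = 0.3 |
|---|---|---|---|---|
| 50 | 0.28 | 11% | 29% | 56% |
| 100 | 0.20 | 17% | 52% | 85% |
| 198 | 0.14 | 29% | 80% | 99% |

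The nominal rate is 5%. For example, with N = 100 and b = 0.2, b√N = 2.0, and Φ(0.04) + Φ(−3.96) = 0.52. The largest N is the planned number of completers and would apply only if every one of them had both scans.

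**6. The correlation with AHI.** A shift that is the same for everyone leaves a correlation unchanged. Bias arises only if the reading moves with the AHI the reader knows. With VVI and AHI standardised, true correlation r, and a reading that moves c SD per SD of AHI, the recorded correlation is (r + c)/√(1 + 2rc + c²), which is not zero when r = 0. The documents give no value for c.

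**The case against.** The strongest reply is that the documents are silent on masking. A reader might infer that the cardiologist is unmasked and that expectation does enter the result. The text does not say so. The numbers come from software, and the plan does not state how far they depend on the operator or what the workstation displays. This stands: expectation could enter, and no more can be claimed.

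Three further inferences are tempting and are not supported:

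- **That the echo effect size is meant to size later trials.** Appendix IV, section C, says "this will lead to the design and implementation of larger studies to evaluate the effect of this AUTOPAP intervention", but the condition in that sentence is improvement in biomarkers and ambulatory blood pressure. Echo is not named, so no follow-on sample size should be hung on it.
- **That the reader must be masked to race.** The VVI correlations are assessed within groups, and no race contrast in VVI is planned. Visit and AHI are the items that matter.
- **That a reader shift could never be disentangled later.** If the loops are stored, a masked re-read remains possible after the study.

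The AHI part is also weaker than the visit part. Section 3 schedules the echo from visit 1, while AHI is known only after the portable monitoring test, so some baseline scans may be read before any AHI exists. That protection is accidental and incomplete, since the baseline scan may be done later.

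Finally, the endpoints are exploratory, and an uncontrolled change stays uncontrolled after masking. Both statements are true. They limit the importance of the point, but they give no reason to leave a cheap safeguard out.

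**Conclusion.** The point holds as a gap in specification with a plausible route to bias. A study collaborator reads the VVI data, masking to visit or AHI is not provided for, and scan order reveals treatment. The exploratory pre-post VVI effect size and the VVI-AHI correlation are therefore open to reader expectation.

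The size cannot be derived from the documents. What can be said is that a systematic shift of b SD adds b to the standardised pre-post effect. Under the assumed shifts of 0.1 to 0.3 SD, this is of the same order as the sampling error, and the confidence interval would not reveal it. These figures show sensitivity and are not evidence that a shift will occur.

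The primary outcome, 24-hour ambulatory blood pressure, is recorded by a device and is not touched. Masking would remove one source of bias and would not stand in for an untreated control. This is a minor, inexpensive improvement.

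**What to change.** In Section 3, item viii, add that:

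- research VVI measurements are made from stored loops coded by study ID, with visit date and AHI removed;
- the same cardiologist reads them in random order;
- where a patient has both scans, the two are read in the same session;
- patients with only a baseline scan are coded and mixed into the same sessions, so that they still contribute to the AHI correlation;
- clinical echo reports are issued separately, as usual.

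The baseline-only rule is needed because echo is optional and Section 9.4.1 expects 10-20% attrition. A rule that reads complete pairs only would strand scans that the AHI correlation can use.

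The cost is the relabelling work and research readings that wait until a patient's scans are complete. No extra scan or reader is needed. The change assumes that loops can be stored and analysed with the identifying fields hidden. The documents do not say so, and the echocardiography laboratory should confirm it before the text is adopted.

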---	---

	will be given instructions regarding follow-up care for OSA with sleep medicine or primary care provider.
Duration of Patient Participation:	Visits 1- 3 over 7-10 days Visits 4-5 over 90-100 days
Study Duration:	Total duration: 100-110 days (4 months)
Number of Patients to initiate AUTOPAP Treatment:	220 Our sample calculations and current dropout rate 2/16 (12.5%, lower than the anticipated 20%) suggest n = 220 will provide 80% power to detect between group difference at two-sided alpha of 0.05.
Eligibility Criteria:	
Inclusion Criteria:
 
 1. Self-identified African American and Other Veterans 2. Age: 18-70 years 3. Hypertension 4. Apnea hypopnea index (AHI) ≥ 15/hour on portable monitoring (PM) 
RATIONALE ** We have modified inclusion criteria from self-identified African American and European American Veterans to African American and “Other” for the following reasons:
 
 • Our primary goal is to identify treatment response in AA compared to other race (Hypothesis: response of hypertension to AUTOPAP treatment will be higher in AA than other groups). • To improve recruitment for this study and meet target enrollment (n = 220) over next two years. 
Exclusion criteria:
 
 1. Past/current treatment of OSA or other primary sleep disorders 2. Active uncontrolled medical or psychiatric conditions 3. Shift work in preceding 6 months 4. Current illegal drug or daily alcohol use 5. Pregnancy
Treatment Effectiveness Endpoints:	
 1. Change in 24-hour ABP measures from baseline to after 3 months of AUTOPAP treatment. 2. Change in CABP measures from baseline to after 3 months of AUTOPAP treatment. 3. Change in 24-hour urinary catecholamine’s and 8-isoprostane measures from baseline to after 3 months of AUTOPAP treatment. 4. RATIONALE ** We have changed CPAP to AUTOPAP treatment as this treatment can be instituted after PM testing and eliminates the need for polysomnography guided CPAP titration. Moreover, AUTOPAP has been shown to equivalent in efficacy to CPAP in terms of symptom resolution and systemic blood pressure response.
Sleepiness as Moderators of Effectiveness:	
 5. Test association of baseline ESS and PVT with effectiveness endpoints 1 to 3. 6. Test association of change in ESS and PVT from baseline to visit 5 with effectiveness endpoints 1 to 3.

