Visit #3: Patients will return to the clinic for AUTOPAP treatment set-up and education by trained study coordinator. Patients and their bed partner will receive a one-on-one standardized education session describing the method of applying the device and individualized mask fitting will be performed; (4) patients will be called twice weekly in the first two weeks and once weekly thereafter to troubleshoot barriers to AUTOPAP use and encourage daily treatment application including during daytime naps.

Visit #4: Patients will return to clinic for repeat PVT, FOSQ, ESS, CABP measurements and to initiate 24-hour ABP and urine collection. Patients will also be scheduled for repeat echocardiography test in the following 3 months, if they had a pre-treatment echocardiography (to assess AUTOPAP treatment effects). No caffeine will be permitted during visits 1 and 5 to minimize interference with EDS assessments. Patients will also do venous blood sampling (35 mL) for processing (DNA, RNA, serum, and plasma) and storage at UI Biorepository

Final Visit # 5: Patients will return to clinic in the morning after initiating 24-hour ABP and urine collection, which will be collected and processed/downloaded. AUTOPAP devices contain a software system that records the duration of AUTOPAP use each day. These data will be accessed and recorded as final measure of AUTOPAP treatment adherence.

Patients will be given instructions regarding follow-up care for OSA with sleep medicine or primary care provider.

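### Stale visit numbers leave the caffeine rule and the baseline-echo deadline out of step with the five-visit text; separately, the repeat-echo window and the change-in-AHI correlation do not fit the planned measurements

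*Combined protocol and SAP*

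**What the plan says.** Section 3 removes the former polysomnography visit and describes five visits. At Visit 3, "Patients will return to the clinic for AUTOPAP treatment set-up and education by trained study coordinator". At Visit 4, "Patients will return to clinic for repeat PVT, FOSQ, ESS, CABP measurements and to initiate 24-hour ABP and urine collection". Visit 5 is the next-morning collection and download, with no PVT or ESS listed. The synopsis visit descriptions agree.

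Other operative text uses different numbers:

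- **Caffeine.** The Visit 4 paragraph of Section 3 says: "No caffeine will be permitted during visits 1 and 5 to minimize interference with EDS assessments".
- **Post-treatment PVT.** The synopsis list of sleepiness moderators and Appendix I both place it at Visit 5. Appendix I has six visits, with AUTOPAP starting at Visit 4.
- **First echo.** Under Visit 1, Section 3 requires it before Visit 4. The opening of Section 3 lists echocardiography among the pre-treatment measurements.
- **Repeat echo.** It is scheduled at Visit 4 as a "repeat echocardiography test in the following 3 months, if they had a pre-treatment echocardiography (to assess AUTOPAP treatment effects". The synopsis defines the endpoint as the change in myocardial mechanics over 3 months of AUTOPAP, and its design paragraph says: "All outcomes assessment will be done 3 months after AUTOPAP treatment initiation".
- **AHI.** Section 9.4.2 plans to correlate change in velocity vector imaging (VVI) with change in AHI. Appendix I determines AHI once, from the diagnostic portable monitoring. On device data, Section 3 says: "AUTOPAP devices contain a software system that records the duration of AUTOPAP use each day".

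**The concern.** Change in PVT lapses is the Aim 2 primary outcome (Section 8) and is also correlated with the blood pressure changes. A caffeine rule meant to protect that measure should apply at both ends of the change score. Read with the current visit descriptions, it applies only at baseline.

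A first echo done on treatment is not a baseline. If the Visit 4 condition is enforced, that patient gets no repeat echo. If it is not enforced, the change score misses part of the treatment effect. A repeat echo late in its window measures about twice the stated treatment period. A correlation with change in AHI has no second AHI to use.

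**Working it through.** **1. Visit numbers side by side**

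| Event | Visit descriptions (synopsis, Section 3) | Appendix I |
|---|---|---|
| AUTOPAP set-up | 3 | 4 |
| Post-treatment PVT | 4 | 5 |
| Final download | 5 | 6 |

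From set-up onward, each Appendix I number is one higher (4→3, 5→4, 6→5). Translated this way, a caffeine rule at Visits 1 and 5 becomes Visits 1 and 4, and an echo deadline before Visit 4 becomes before Visit 3, which is before set-up. The single shift explains both contradictions. They also appear in running prose, so they do not depend on how the Appendix I table was extracted.

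**2. What the caffeine mismatch can do**

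In each group, let p be the share of patients who take caffeine before the post-treatment PVT and c its mean effect on lapses.

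- Shift in the between-group difference in mean change = p_AA × c_AA − p_Other × c_Other.
- If p and c are equal in the two groups, the shift is zero. A constant shift for everyone also leaves the correlations unchanged.
- If only some patients take caffeine, with a common effect c unrelated to their underlying change, the variance of the change score rises by p(1 − p)c².

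The documents give no value for p or c, so no size can be computed. Section 4.2 excludes only average intake above 500 mg/day, so caffeine users are eligible.

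**3. Days on AUTOPAP at Visit 4**

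The synopsis gives "Visits 1- 3 over 7-10 days Visits 4-5 over 90-100 days" and a total of 100-110 days. Since outcomes are set at 3 months after AUTOPAP initiation, I take the 90-100 days as running from set-up.

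- Check: 7 + 90 = 97 and 10 + 100 = 110, against the stated 100-110. The upper end matches; the lower is 3 days short.
- If 90-100 refers to Visit 5, Visit 4 is the day before: 90 − 1 = 89 to 100 − 1 = 99.
- If it refers to Visit 4 itself: 90 to 100.
- Both readings together: 89-100 days. This is how far into treatment the written deadline for the first echo falls.

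**4. Latest repeat echo under the Visit 4 wording**

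Taking 3 months as 91 days (assumption):

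- 89 + 91 = 180 and 100 + 91 = 191 days after set-up.
- 180/91 = 1.98 and 191/91 = 2.10 times the stated 3 months.
- Counted from Visit 1: 7 + 180 = 187 and 10 + 191 = 201 days, against a stated participation of 100-110.

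**5. Change in AHI**

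A change needs two values per patient. The plan schedules one AHI, before treatment. No post-treatment portable monitoring is planned, and the device variable named is duration of use. Nor is this correlation among the goals in the synopsis exploratory endpoints or the Section 8 table, which list only VVI against AHI and effect-size estimates for VVI.

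**6. Other numbers to reconcile (minor)**

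- Repeat blood draw at Visit 5 (Section 2.3, Appendix III), against Visit 4 in Section 3.
- Central aortic pressure at Visits 1 and 5 in the Section 3 measures list, against Visit 4 in the visit text.
- Polysomnography still shown as Visit 3 in the opening of Section 3.
- Pharmacy confirmation at Visit 6 and medication possession ratio at Visits 6 and 8 (Section 5). Visit 8 is in neither scheme.
- Adverse event recording to Visit 6 (Section 7.2.1).
- Start of baseline ambulatory pressure and urine collection: completion of Visit 1, the morning before the monitoring night, or Visit 2 (two places in Section 3, and Appendix I). Every version is pre-treatment.

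**The case against.** The strongest reply is that these are editorial leftovers whose intent can be recovered. Much of that stands.

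- **Caffeine.** The sentence sits in the Visit 4 paragraph and states its purpose, so a matched rule was evidently meant. The synopsis moderator list and Appendix I put the PVT at Visit 5, where the rule would apply. The gap therefore exists only if the current visit descriptions govern. The rule also speaks only of caffeine during visits, not before arrival, so the contrast between restricted and unrestricted sessions may be smaller than it looks. A reader might infer that the Aim 2 comparison is biased. The documents do not show that: bias needs a difference between groups in caffeine use or effect, and no figure for either is given.
- **First echo.** A reader might infer that the plan authorises an on-treatment baseline. It does not: Section 3 twice treats this echo as pre-treatment. The fault is that the only explicit deadline conflicts with that intent.
- **Repeat echo.** A reader might say that an echo at six months is permitted. The Visit 4 wording allows it, but the 3-month outcome rule and the stated participation time contradict it. This is a conflict, not a permission.
- **Upper bounds.** Pairing the earliest set-up (day 7) with the latest final visit (day 110) gives 103 days to Visit 5 and larger bounds. That falls outside the 90-100 days the calculation assumes.
- **Change in AHI.** No listed endpoint is lost, because the correlation appears only in Section 9.4.2.
- **Remaining numbers.** Most have recoverable meaning. For example, Section 3 places the closing medication record at the final visit, and the synopsis and Section 3 both eliminate polysomnography.

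What survives is that staff who follow the written visit numbers would depart from the plan's own intent at the caffeine rule and the first echo. The repeat-echo window and the AHI correlation are not explained by renumbering at all.

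**Conclusion.** The point holds in conditional form and should be fixed.

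1. If the current visit descriptions govern, the caffeine rule covers the baseline PVT and misses the post-treatment PVT. This touches the Aim 2 primary outcome; its size is unknown.
2. The stated deadline for the first echo falls about 89-100 days after AUTOPAP set-up, in conflict with its pre-treatment purpose.
3. The repeat-echo window extends to about 180-191 days, roughly twice the 3-month endpoint.
4. Change in AHI cannot be computed for any patient from the planned measurements.

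Items 2 to 4 affect exploratory endpoints only. The figures assume that the 90-100 days run from set-up and that 3 months is 91 days. Nothing here alters the Aim 1 primary comparison or the sample size. The remaining visit-number conflicts are minor.

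**What to change.** - Adopt one visit scheme throughout and correct the synopsis, Sections 2.3, 3, 5 and 7.2.1, and Appendices I and III to match it.
- Tie the caffeine restriction to every PVT session instead of to visit numbers.
- State that the baseline echo is completed before AUTOPAP set-up.
- Give the repeat echo a stated window around the 3-month visit.
- Drop the change-in-AHI correlation from Section 9.4.2; the listed goals do not need it.
- Assign the medication possession ratio and pharmacy check to visits that exist, and reconcile the three descriptions of when baseline ambulatory pressure and urine collection start.

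The cost is an amendment of wording and one exploratory correlation removed, with no new procedures. The one practical downside is tighter echo scheduling.
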